## **Specific Aims:**

1. The primary goal of this study is to compare the CLD and DE symptoms of moderate to severe DE subjects between 30 days of Tangible Hydra-Peg treated scleral lens wear and 30 days of untreated scleral lens wear.  
Hypothesis: CLD and DE symptoms will be significantly better after 30 days of Hydra-Peg treated scleral lens wear as compared to 30 days of untreated scleral lens wear.
2. The secondary goal of this study is compare the CLD and DE signs of moderate to severe DE subjects between 30 days of Tangible Hydra-Peg treated scleral lens wear and 30 days of untreated scleral lens wear in DE subjects. As DE can impact vision quality and Hydra-Peg may impact contact lens wearing times, as a subanalysis, we will also examine contact lens wearing times and quality of vision such as frequency of foggy vision between treated and untreated scleral lens wear.

Hypothesis: CLD and DE signs will be significantly better after 30 days of Hydra-Peg treated scleral lens wear as compared to 30 days of untreated scleral lens wear. Frequency of foggy vision and contact lens wearing time will be significantly better after 30 days of Hydra-Peg treated scleral lens wear as compared to 30 days of untreated scleral lens wear.

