### Experimental Design

30 subjects with symptomatic moderate to severe dry eye and symptoms of CLD will complete a double-masked cross-over study. The participants will be randomly chosen to wear their habitual untreated scleral lenses or Hydra-Peg treated scleral lenses first for 30 days. Half of the participants (15) will be randomly chosen to wear the Hydra-Peg treated scleral lenses first for 30 days, and the other half of the participants (15) will be chosen to wear their habitual untreated scleral lenses for 30 days first. One week wash-out periods with no lens wear will be placed before and between the 30-day test periods. The OSDI, CLDEQ-8, a battery of dry eye diagnostic tests, and tests which will assess the impact of contact lenses on the ocular surface will be administered from 3:00 to 5:00 pm at baseline, after the first test period, and after the cross-over. Contact lens wearing time and questions related to quality of vision will also be collected at baseline, after the first test period, and after the cross-over.

The battery of clinical dry eye sensitive tests will include, TBUT of the ocular surface, and ocular surface staining. TBUT over the surface of the scleral lenses, lid wiper epitheliopathy (LWE), and contact lens-related papillary conjunctivitis we will also be examined as they these factors may change with alteration of a contact lens surface.

The study will be double-masked. Lens pairs will be supplied in identical cases, differing only by code mark unknown to the tester. Only one lens pair during the respective test period (treated or untreated) will be given to each participant. The general study schedule following recruitment is described below.

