## Statistical Analysis

The key values used for analysis in this study will be differences in CLD and DE symptoms following scleral lens wear with Tangible Hydra-Peg and that found after untreated scleral lens wear. In addition, we will examine differences in CLD and DE signs between Tangible Hydra-Peg scleral lens wear and untreated scleral lens wear. Preliminary data analyses will include inspection for kurtosis and skewness of each distribution and test for normality, using the Shapiro-Wilk test. Normal distributions will be analyzed using a paired t-test. Non-normal distributions will be analyzed with the Wilcoxon Signed Ranked test.

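### A normality pre-test with no stated level or target chooses the test for each outcome, so the effect being tested on the primary symptom scores is not fixed in advance

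*Combined protocol and SAP*

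**What the plan says.** The Statistical Analysis section is the whole analysis plan. It opens by naming what will be analysed: "The key values used for analysis in this study will be differences in CLD and DE symptoms following scleral lens wear with Tangible Hydra-Peg", compared with untreated wear. It then calls for "inspection for kurtosis and skewness of each distribution and test for normality, using the Shapiro-Wilk test", and the result decides the test: "Normal distributions will be analyzed using a paired t-test. Non-normal distributions will be analyzed with the Wilcoxon Signed Ranked test".

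The section does not give:
- a significance level for the pre-test, or a rule for weighing it against the inspection of skewness and kurtosis;
- a definition of the distributions to be inspected (paired differences, or scores under each lens);
- an effect measure, such as a mean or a median difference;
- a fixed primary test, or a sensitivity analysis.

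Specific Aims states the primary hypothesis only as "CLD and DE symptoms will be significantly better after 30 days of Hydra-Peg treated scleral lens wear" than after untreated wear. Experimental Design gives the size and structure: "30 subjects with symptomatic moderate to severe dry eye and symptoms of CLD will complete a double-masked cross-over study", and "Half of the participants (15) will be randomly chosen to wear the Hydra-Peg treated scleral lenses first for 30 days".

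**The concern.** The two candidate tests answer the same question only when the paired differences are symmetric. The t-test addresses the mean difference. The signed-rank test addresses the centre of a symmetric distribution, and under skew it is a test of neither the mean nor the median. Skewed differences are among those that Shapiro-Wilk picks out, so the rule tends to send them to the test whose reading then becomes unclear.

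The primary aim rests on two questionnaires, OSDI and CLDEQ-8. Under this rule one may be reported as a mean difference and the other by ranks, with the choice made by a preliminary test on 30 values. A reader could not say beforehand which effect the trial set out to test.

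**Working it through.** The documents contain no alpha, power, SD or distribution for either score, so there is no planned figure to reproduce. The check is a simulation of how the rule behaves.

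**Inputs from the documents.** n = 30 paired differences; 15 participants per sequence; Shapiro-Wilk, then a paired t-test or a signed-rank test.

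**Assumptions.** Main test two-sided at 0.05; pre-test failed when p < 0.05; signed-rank test by normal approximation.

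**Set-up.** For each person d = treated minus untreated. The t-test uses mean(d) / (s/√30) on 29 df. Skewed differences are gamma with shape k, minus their mean k, giving skewness 2/√k: k = 8, 4, 2, 1 gives 0.71, 1.00, 1.41, 2.00.

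**Step 1. True mean difference zero, effect varying between people (20,000 runs each).**

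| Shape of differences | Fails pre-test | Planned rule rejects | Fixed t-test rejects |
|---|---|---|---|
| Normal | 5% | 5.3% | 5.3% |
| Skewness 0.71 | 25% | 6.4% | 5.3% |
| Skewness 1.00 | 45% | 7.9% | 5.7% |
| Skewness 1.41 | 75% | 10.7% | 6.2% |
| Skewness 2.00 | 97% | 15.7% | 6.8% |

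Separate runs of 6,000 gave 7.6% against 5.5% at skewness 1.0, and 15.4% against 7.0% at 2.0.

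**Step 2. True median difference zero.** The planned rule rejects 7.6%, 9.1%, 11.4% and 14.1% at the four skewness values. It is not a clean test of the median either.

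**Step 3. Two scores, two tests.** If a score fails the pre-test with probability p, and the two scores behave independently, they get different tests with probability 2p(1 − p). At p = 0.25 this is 2 × 0.25 × 0.75 = 0.375; at p = 0.45 it is 2 × 0.45 × 0.55 = 0.495. Correlation between the scores would lower this, and unequal skewness could raise it.

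**Step 4. No effect in anyone.** With skewed but exchangeable scores under the two lenses, the differences are symmetric about zero. The rule rejects 5.3% with the pre-test on differences and 5.2% with it on the scores under each lens. With symmetric heavy tails (t, 3 df) it rejects 5.1%.

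**Step 5. Power with a true shift of 0.55 SD.**

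| Shape of differences | Planned rule | Fixed t-test | Rule minus t-test |
|---|---|---|---|
| Skewness 0.71, a few strong improvers | 83.0% | 86.0% | −3.0 |
| Skewness 1.0, a few strong improvers | 81.5% | 87.9% | −6.4 |
| Skewness 2.0, a few strong improvers | 77% | 94% | −17 |
| Skewness 2.0 mirrored, a few who worsen | 89% | 78% | +11 |
| Heavy symmetric tails | 95% | 86% | +9 |

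**The case against.** The strongest reply is that the rule does no harm to the null that matters. Order is randomised, so if the coating changes nothing for anyone the paired differences are symmetric apart from period effects, and the signed-rank test keeps its level. Step 4 confirms this, and the point stands. A reader might infer from the 15.7% in Step 1 that an ineffective coating would be declared effective that often. The documents do not support that: the figure describes a coating that helps some wearers and sets others back with a zero average, and the stated hypothesis does not commit to a mean.

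A second tempting inference is that the rule costs power. Step 5 shows the direction depends on which way the differences are skewed, so no consistent loss can be claimed.

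A third is that the pre-test is applied to the scores under each lens, which would check the wrong quantity and leave no rule when one lens passes and the other fails. The wording allows this, but the section's opening sentence makes the differences the quantity analysed, which is the more natural reading. Even on the other reading the error rate is barely touched. With normal differences and skewed scores, 91% of trials go to the signed-rank test without need, yet the rejection rate is 5.0%.

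Finally, skewness of 2 is severe and assumed. At 0.71 the gap in Step 1 is about one percentage point, and at 2.0 the fixed t-test also exceeds 5%. This limits the size of the point. It does not supply the missing level, target or effect measure.

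**Conclusion.** The point holds in a limited form. The plan does not fix which test, and hence which effect, answers the primary aim. At n = 30 the deciding pre-test is unstable under moderate skew, close to a coin toss at skewness 1.0. As a test of a zero mean difference under a varying effect, the rule's rejection rate runs from about 6% at skewness 0.71 to 15–16% at 2.0, against about 5% to 7% for a fixed t-test. With no effect in anyone both hold about 5%, and power may rise or fall.

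These sizes rest on assumed shapes, a two-sided 0.05 test and a 0.05 pre-test, none of which the documents state. The case for change is mainly prespecification: the data should not choose the effect measure for the two symptom scores. It is worth correcting, but it does not invalidate the design.

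**What to change.** - For OSDI and CLDEQ-8, drop the pre-test. Prespecify the mean within-person difference (treated minus untreated) with a 95% CI and a t-based test at a stated level, adjusted for period through the randomised 15/15 sequence. The estimate is the average of the two sequence means of d; its standard error uses the pooled within-sequence SD on 28 df.
- Report the signed-rank test with a Hodges-Lehmann estimate as a fixed sensitivity analysis, whatever the distribution looks like.
- For graded signs and foggy-vision frequency, choose rank methods now, by type of scale.
- Keep Shapiro-Wilk, skewness and kurtosis as descriptive checks, on the paired differences only.

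**Cost.** A few lines of text, and one degree of freedom for period (29 to 28). Relative to the planned rule, power is lost if the differences have heavy symmetric tails (95 − 86 = about 9 points in the case tried) or are skewed towards a few who worsen (about 2 to 12 points across the skewness range).

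**Period adjustment.** The pre-test does not cause its absence, but the same sentence can supply it. Suppose period moves each difference by 0.5 SD, in opposite directions in the two sequences. The unadjusted variance becomes 1 + 0.5² = 1.25, so a 0.55 SD shift shrinks to 0.55/√1.25 = 0.49 SD. Adjustment raises power from 76% to 83%. The size of the period effect is an assumption.
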